9.3.3 PROTOCOL SPECIFIC REPORTING INFORMATION

For the purpose of this protocol, mild (i.e., clinically non-significant) hypoglycemia and hyperglycemia symptoms or blood glucose values out of the normal range will not be reported as adverse events unless determined to meet the criteria of a Serious Adverse Event.

9.4 DEVICE DEFICIENCIES

All device deficiencies related to the identity, quality, durability, reliability, safety, or performance of an investigational medical device shall be documented throughout the clinical investigation and appropriately managed by the Sponsor. Device deficiencies include malfunctions, use errors, and inadequate labeling.

10 SOURCE DOCUMENTATION, CASE REPORT FORMS AND DATA MANAGEMENT

Data in this study will be collected on Case Report Forms (electronic or paper) as well as electronic file transfers.

10.1 SOURCE DOCUMENTS AND CASE REPORT FORMS

The investigator or his/her designee at each site is responsible for recording investigation-related data onto the CRFs and maintain source documentation supporting the data. Good Clinical Practice in the documentation on source documents and CRFs will be followed. For source documentation or if papers CRFs are used, the data must be legibly written in ink. If changes are required, a single line is to be drawn through the incorrect information, the correct information written in and the change initialed and dated by the individual making the change. The reason for correction may be noted, unless obvious. Pencil, correction fluid or correction tape must not be used, and incorrect information must not be obscured (scribbled-out).

The investigator must review, sign, and date the CRFs as indicated on the form or electronically; these responsibilities cannot be delegated to another person. It is the investigator's responsibility to comply with regulatory requirements including, but not limited to, the maintenance of accurate, complete and current records relating to the CRFs.

The Sponsor (or their designee) will review the data against the original source documents and ensure any noted discrepancies are resolved by the investigational site. Subject data will be compared to information originally recorded on source documents related to the trial (i.e. professional notes, laboratory reports, investigation-specific worksheets, etc.).

Investigation-related information collected on CRFs will be entered into a secure database. The database design and installation will be validated prior to use.

Validation techniques used by Senseonics are consistent with applicable regulations and guidelines. Each database must pass a series of standard tests that demonstrate the usability and correctness of the database system to approved specifications. The test process generates detailed test result logs, which are provided as part of the database documentation.

The details of data review, database cleaning and data querying are described in a Data Quality and Management Plan (DQMP). This plan is updated throughout the investigation as amended data management requirements and investigation-specific data conventions are determined.

A comprehensive EDC User Guideline will be developed for participating investigational sites describing general instructions on CRF completion; this guideline also includes investigation- specific data entry, and query management instructions.

Data entered by investigational sites will be reviewed by the Sponsor or their designee on an ongoing basis to ensure adequate query resolution and identify and query adverse events, protocol deviations, and any other ambiguous data points.

10.2 GLUCOSE MEASUREMENT DATA FLOW PROCESS

10.2.1 TRANSMITTER DATA LOGGING

The Transmitter is a rechargeable, external device worn over the Sensor insertion site that supplies power to the Sensor. The Transmitter periodically (usually every 5 minutes) reads sensor data and calculates sensor glucose and trends. The information from the Transmitter is then transmitted for display to a handheld device (e.g. Smartphone) via Bluetooth Low Energy with AES-CCM encryption. At any one time, the Transmitter contains all of the data collected since last erasure, extending back in time to the limit of its capacity. Each Sensor reading is recorded with a timestamp. Successive uploads from a subject's assigned Transmitter can be assembled into a cumulative time profile, using these timestamps.

10.2.2 TRANSMITTER DATA RETRIEVAL

Data from Subject Assigned Transmitters will be collected at clinic visits. The data will be downloaded by a data communication device running Senseonics' custom software application and saved to a file. The file will be uploaded to a 21CFR11 compliant record, utilizing a 21CFR11- compliant third-party software application.

The Senseonics' software application will identify the Sensor serial number and ask the user to enter the site ID, subject ID and visit number. The file name will include these identifiers as well as the download date and time. Transmitter data will also be uploaded to a data management system to monitor calibration compliance.

Incomplete or missing data downloads that cannot be used in the analysis or cannot be made available at a future visit would be considered missing data for the purpose of analysis for the corresponding time interval.

10.2.3 REFERENCE GLUCOSE ANALYZER DATA

Plasma glucose data will be recorded by a YSI Analyzer and recorded on Source Document Forms. This data will be transferred to a 21CFR11-compliant electronic record system. Paper strip records and/or electronic records collected from the YSI Reference Glucose Analyzer will be retained according to GCP. Printouts should be labeled, including a patient identifier, sample number, and operator initials, and either photocopied or scanned.

10.2.4 BLOOD GLUCOSE METER DATA

Data from the study Subject SMBG Meters will be uploaded at clinic visits and electronically transferred to a 21CFR11-compliant electronic record system.

Incomplete data downloads that cannot be used in the analysis or cannot be made available at a future download would be considered missing data for the purpose of analysis for the corresponding time interval.

10.2.5 DATA RETENTION

During and/or at the conclusion of the investigation, original data from the laptop at the clinical site will be transferred to a 21CFR11-compliant electronic record system. The clinical site will be provided a master CD/USB of the electronic data to meet record retention requirements.

11 STATISTICAL METHODS

11.1 STATISTICAL ANALYSIS OVERVIEW

11.1.1 GENERAL CONSIDERATIONS

The statistical analysis of the data is focused on assessing performance via downloads and data from the clinic including the Fingerstick Blood Glucose Meter Data (Subject SMBG), the YSI Reference Glucose Data, the Eversense® 180 CGM System Data, and other manual

entries (e.g. Implant Time, Subject Number). Descriptive statistics will be used to summarize all subject Baseline and outcome data collected during the study. Continuous variables will be summarized using means, standard deviations, and ranges. Categorical variables will be summarized in frequency distributions.

Statistical analyses will be performed by validated software (e.g., MATLAB and SAS® 9.4). Adequate source document verification and/or audit activities will be utilized to assess the validity of investigation conclusions. Copies of databases used to prepare clinical report summaries will be archived to enable any statistical analyses performed to be replicated.

11.1.2 DATA POOLING

Subjects will be selected consecutively (i.e., selecting every subject in the order they present at the site) among those who meet the inclusion/exclusion criteria. All subjects will receive sensors and transmitters. The primary effectiveness measure (MARD) will be analyzed with data pooling across sites. Site effects will be examined, but only descriptively.

Analyses will be performed based on aggregating all patients in the study, and again separately for each randomized groups. The analysis by randomized groups will be only performed descriptively and there will be no formal statistical comparisons. Transmitters will be designated as primary (left arm) and secondary (right arm).

Analyses will be performed for subgroup of interest (based on type of diabetes (type I vs. type 2), age (\geq 65 years of age vs. $<$ 65), and baseline HbA1c (\geq 8% vs. $<$ 8%).

11.1.3 SENSOR EVALUATION PERIOD

The Eversense® 180 CGM System performance will be evaluated in the period after insertion. The Transmitter will assess the Sensor's signal sensitivity in real time for any premature failure independent of the expected lifetime based on time from insertion. If the measurement of potential degraded response of the Sensor optical system signal drops below a pre-defined percent of its original value and/or systemic patterns in Sensor accuracy to entered calibration points drops below a pre-defined threshold, then the device has reached its end of life (sensor retirement) and will no longer provide glucose readings. This end of life determination marks the end of the accuracy evaluation period for this Sensor. The distribution of times between Sensor insertion and end of life or completion of scheduled study visits, whichever occurs first will be summarized.

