5.4 PRIMARY SENSOR BLINDING

During the study the primary system may go into a “blinded mode” (called Clinical Mode by the device). Under these circumstances subjects will continue to wear the system, and enter calibrations (as prompted) and SMBG values, but the system will not provide sensor glucose information or glucose related alerts. Subjects should continue with all remaining sensor accuracy visits with the blinded system.

If a primary sensor displays a “sensor replacement” alert, it (and the secondary sensor if applicable) will be removed at an unscheduled visit, and the subject will be withdrawn.

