3.2.3 Other safety endpoints

1. Incidence of all device-related or sensor insertion/removal procedure-related adverse events in the clinic and during home use.
2. Incidence of all adverse events in the clinic and during home use.
3. Incidence of hospitalizations due to hypoglycemia, hyperglycemia or ketoacidosis occurring during home use.
4. Incidence of reported hypoglycemic and hyperglycemic events occurring during home use.

4 Study Design

This is a prospective study involving around 210 participants across 15 study sites in the United States. Approximately 180 participants will have a Sensor inserted into their arm, of which, at least 80 will have two Sensors inserted (one in each arm).

Participants need to attend 12 visits over a period of about eight months. At each clinic visit, the accuracy of the Eversense® 180 CGM System is evaluated by comparing glucose concentrations recorded by the Sensor with blood glucose concentrations from a bedside glucose analyzer. Most participants also undergo supervised hypoglycemia and hyperglycemia challenges during a visit.

Care decisions are based on self-monitoring blood glucose (fingerstick) tests and usual standard medical practice, and not on Eversense® 180 CGM System results.

The study population includes adults with Type 1 or Type 2 diabetes mellitus. This study takes approximately 12 months to complete, inclusive of the enrollment period.

A subgroup of subjects received a modified indicator hydrogel which includes the addition of a new monomer, 4-vinylphenylboronic acid. The VPBA monomer serves as a sacrificial boronic acid that reacts with reactive oxygen species (ROS) generated during the body's normal healing response to Sensor insertion without affecting the glucose recognition element, thereby increasing the longevity of the Sensor *in vivo*. Internally, the modified hydrogel indicator is referred to as the "sacrificial

Statistical Analysis Plan		Page 9 of 28
Sponsor Senseonics, Incorporated	Study PROMISE Study: A Prospective, Multicenter Evaluation of Accuracy and Safety of an Implantable Continuous Glucose Sensor Lasting up to 180 Days	Version 3.0

boronic acid – SBA” hydrogel, hence the modified Sensor is referred to as the “SBA Sensor” in this document.

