An enrollment target of 20 participants per subgroup of interest (see Section 6.9) should provide sufficient data to characterize these subgroups. The probability of detecting one or more events in a group of 20 participants is 80%, when such event occurs with a probability of 8%.

For the SBA sensor configuration, a total of 43 sensors are planned.

Statistical Analysis Plan		Page 13 of 28
Sponsor Senseonics, Incorporated	Study PROMISE Study: A Prospective, Multicenter Evaluation of Accuracy and Safety of an Implantable Continuous Glucose Sensor Lasting up to 180 Days	Version 3.0

6 Statistical Analyses

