6.3 Handling of Missing Data

All attempts will be made to limit the amount of missing data. Unless otherwise specified, no attempt will be made to impute missing data. If a data point is missing, that data point will not contribute to that portion of the analysis. The number of evaluable observations will be reported in analysis so that extent of missing data can be assessed.

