6.10 Sensor Design Change Analysis

The SBA sensor configuration is of key interest. The following analyses will be performed for the SBA sensor configuration, separately and within subject as appropriate for:

- Primary, secondary and other effectiveness endpoints
- Sensor longevity

Further analysis on an expanded set of sensors that have slower indicator degradation rates will pool data from SBA sensors along with subjects with only primary sensors whose sensors have a degradation that falls within the distribution of degradation for the SBA sensors.

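### Sensor life is summarised without an event indicator or censoring, although some working sensors, including secondaries removed with the primary, leave the study early

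*Protocol*

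**What the plan says.** Protocol 11.1.3 defines end of life as the sensor's signal, its accuracy against calibration points, or both, crossing a pre-set threshold. It then gives the only readable rule for reporting sensor life: "The distribution of times between Sensor insertion and end of life or completion of scheduled study visits, whichever occurs first will be summarized".

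The general methods add nothing specific to time-to-event data. Protocol 11.1.1: "Continuous variables will be summarized using means, standard deviations, and ranges". SAP 6.1.1 adds medians, counts and optional confidence intervals. On missing data, SAP 6.3 says: "If a data point is missing, that data point will not contribute to that portion of the analysis".

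SAP 6.10 introduces the SBA work with "The following analyses will be performed for the SBA sensor configuration, separately and within subject as appropriate for", and one of the items that follows is "Sensor longevity". No definition, event, censoring rule or estimator is given. SAP section 4 describes the modified hydrogel as "thereby increasing the longevity of the Sensor", and SAP section 5 says: "For the SBA sensor configuration, a total of 43 sensors are planned".

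Protocol 5.4 governs a primary sensor that shows a replacement alert: "it (and the secondary sensor if applicable) will be removed at an unscheduled visit, and the subject will be withdrawn". There are exceptions:

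- A primary in Clinical Mode stays in place (5.4).
- If the primary is removed for infection, the secondary becomes the primary (7.3).
- A primary that fails within 30 days is replaced and visits continue (5.3). For an alert in that period, 5.3 and 5.4 point different ways and must be reconciled.

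Protocol 4.2.10 keeps the secondary sensor in place to observe its life for up to 365 days. The SAP was written for protocol Version 7, and the one-year wear came in revision 08.

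**The concern.** The rule in 11.1.3 produces a time but no record of why the time ended. A sensor that failed on day 150 and one that was working when visits finished differ in kind, and means, standard deviations and ranges treat them alike. A sensor taken out while working, through withdrawal, infection or the other arm's alert, reaches neither endpoint named in the rule. The analyst must therefore improvise: count the removal as end of life, drop the sensor, or censor it. These choices can give different answers.

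Linked removal makes this more than a loose end in two-sensor subjects, because one sensor's observed time is ended by the other's failure. SAP 6.10 plans within-subject analysis in which longevity is one item. A life of up to 180 days is the device's intended operating life, and longer life is the stated rationale for the SBA hydrogel, so these summaries are likely to be read closely.

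**Working it through.** **Inputs from the documents.** Neither document gives a sensor-survival figure. The nearest is planned retention in Protocol 11.1.4, and that table reproduces:

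- Per visit, subjects x 42 points: 160 x 42 = 6720; 80 x 42 = 3360; 155 x 42 = 6510; 140 x 42 = 5880; 130 x 42 = 5460. Day 180 uses 50 points: 112 x 50 = 5600 and 120 x 50 = 6000.
- Total: 4 x 6720 + 2 x 3360 + 6510 + 5880 + 5460 = 51450. Adding 5600 or 6000 gives 57050 or 57450, as stated.
- Retention at Day 180: 112/160 = 70% and 120/160 = 75%.

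**Assumptions, not document figures.** The secondary sensor has true Day 180 survival of 90%. Either all or half of planned attrition is primary end of life. Lives within a subject have correlation 0, 0.3 or 0.6. In the simulation, lives are Weibull with shape 2.

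**Step 1. Primary sensors, half the loss due to withdrawal.** With equal constant hazards for failure and withdrawal, Kaplan-Meier survival is the square root of retention.

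| Retention | Withdrawals as failures | Withdrawals dropped | Kaplan-Meier |
|---|---|---|---|
| 112/160 | 70% | 112/(112 + 24) = 82.4% | √0.70 = 83.7% |
| 120/160 | 75% | 120/(120 + 20) = 85.7% | √0.75 = 86.6% |

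Counting withdrawals as failures costs about 12 to 14 points. Dropping them costs about 1.

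**Step 2. Linked removal, independent lives.** The share of secondaries in place and working at Day 180 is the product of the two survival probabilities.

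- All attrition is primary failure: 0.9 x 0.70 = 63% and 0.9 x 0.75 = 67.5%.
- Half is: 0.9 x 0.837 = 75% and 0.9 x 0.866 = 78%.

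**Step 3. Linked removal, correlated lives.** In a simulation of 300,000 sensor pairs, the secondary was removed at the primary's end of life. The second row takes half of a 25% loss, 1 - 0.25/2 = 87.5%. Ranges run over the three correlations.

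| Primary survival | Secondaries removed working | Removal counted as end of life | Removed sensors dropped | Kaplan-Meier, censored at removal |
|---|---|---|---|---|
| 70-75% | 22-29% | 63-72% | 88-93% | 90-94% |
| 87.5% | 10-12% | 79-82% | 89-91% | 90-92% |

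The true value is 90% throughout. In the first row, 22-29% of 43 sensors is about 10-12, if all 43 SBA sensors were secondaries. Mean time within 180 days falls from 174 to 156-162 days when removal counts as end of life. Kaplan-Meier is unbiased at correlation 0 and up to 4 points high at 0.6.

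**Step 4. Within-subject comparison.** If linked removal is recorded as the secondary's life, the recorded time is min(T2, T1), where T1 and T2 are the primary's and secondary's lives. It can never exceed T1 in the same subject, apart from the exceptions in 5.3, 5.4 and 7.3.

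**Step 5. Day 365.** The same Weibull curve gives true survival of 65%. With primaries at 70-75%, and assuming the removal rule also applies to the second primary, the estimates are 31-49% (counted as end of life), 57-74% (dropped) and 65-78% (Kaplan-Meier).

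**The case against.** The plan is silent on censoring; it does not rule it out. The time in 11.1.3 is the usual observed-time variable for a censored analysis, and a working sensor removed under 5.4 has not met the protocol's definition of end of life. If SAP 6.3 were applied and removed sensors were dropped, the Day 180 figure would move only a few points. Removals are partly reported elsewhere: early explants in the accountability diagram (Protocol 11.1.7) and exits by reason (SAP 6.4). Some appendix pages were not available and could contain a sensor-life table. All of this stands. But those reports give counts rather than times, and no readable methods section says which handling applies.

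A reader might infer that SBA longevity will be badly understated, with 63% as the expected figure. The documents do not support that:

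- The figure needs linked removal to be counted as failure, which 11.1.3 does not say.
- It also needs every planned loss to be primary end of life. The 112-120 row is a minimum number of subjects for paired points, not a survival estimate.
- Neither document says which arm carries the SBA sensor. If it is the primary, its comparator is cut short instead.
- Longevity is not among the objectives or endpoints, SAP 6.2 calls the SBA analyses supportive, and section 4 gives a design rationale rather than a formal claim.
- Single-sensor subjects are not exposed to linked removal. In the extension, poor accuracy of the new primary leads to Clinical Mode, which by itself does not trigger removal.

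Nor is simple censoring a complete answer, since it reads high if lives within a subject are correlated.

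**Conclusion.** The gap is real and worth closing before sensor life is analysed. Followed as written, 11.1.3 merges failures with completers and gives no valid place to sensors removed while working; SAP 6.10 supplies no method for SBA longevity; and the SAP has none for 365-day life.

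The size cannot be fixed from the documents. For a secondary with an assumed true 90% survival at Day 180, counting linked removal as end of life gives about 63-72% if all planned attrition is primary failure and about 75-82% if half is. Dropping removed sensors gives about 88-93% across the scenarios. The direction also depends on the handling: the first choice understates life, while dropping can err either way. The Day 365 scenario is wider, but it rests on one more assumption about the second primary. The analyses concerned are descriptive, so no error rate, power or endpoint result is at stake.

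**What to change.** Replace the sentence in Protocol 11.1.3, and add matching text to SAP 6.10, as follows:

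- **Event:** sensor end of life, derived from logged data by one threshold for both sensors. The secondary system calculates no glucose during the study (Protocol 1.1.2), so its end of life must be derived afterwards.
- **Censoring:** right-censor at linked removal, subject withdrawal, other removal (including infection) and completion.
- **Estimate:** Kaplan-Meier survival at 180 days with a 95% confidence interval and counts of sensors by reason for ending, separately for primary, secondary (continued to 365 days) and SBA sensors.
- **Sensitivity analysis:** for two-sensor subjects, repeat the estimate over a range of assumed within-subject correlation, because censoring at linked removal may be informative.
- **SBA placement:** state which arm carries the SBA sensor, so that the within-subject comparison can be interpreted.
- **Reconciliation:** resolve Protocol 5.3 against 5.4 for a replacement alert in the first 30 days, so that the reason for ending is coded one way.

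The cost is wording in two documents and a small amount of standard programming. No new data collection appears to be needed. Intervals will be wider, especially for the 43 SBA sensors.

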11.1.4 EXPECTED PAIRED POINTS BY RANGE*

The expected number of paired YSI/sensor points by YSI glucose range are targeted as follows:

	Day 1	Day 7	Day 14	Day 22	Day 30	Day 60	Day 90	Day 120	Day 150	Day 180	Total through 180 days
YSI Range / Min # of subjects	160	80	80	160	160	160	155	140	130	112-120	
40-70 mg/dL	1040	520	520	1040	1040	1040	1008	910	845	728-780	8691-8743
71-299 mg/dL	4400	2200	2200	4400	4400	4400	4263	3850	3575	3976-4260	37664-37948
300-400 mg/dL	1280	640	640	1280	1280	1280	1240	1120	1040	896-960	10696-10760
Total	6720	3360	3360	6720	6720	6720	6510	5880	5460	5600-6000	57050-57450
										Total paired points	57050-57450

*Estimates based on 160 subjects inserted, with challenge type distributed equally

